7.2.2. Assessment of Severity

The severity of AEs will be graded using the modified Common Terminology Criteria for Adverse Events (CTCAE), version 4.03. For each episode, the highest grade attained should be reported.

If a CTCAE criterion does not exist, the investigator should use the grade or adjectives: Grade 1 (mild), Grade 2 (moderate), Grade 3 (severe), Grade 4 (life-threatening) or Grade 5 (fatal) to describe the maximum intensity of the adverse event.

For purposes of consistency with the CTCAE, these intensity grades are defined in [Table 7-1](#) and [Appendix 4](#).

Table 7-1. Grading of Adverse Event Severity

Grade	Adjective	Description
Grade 1	Mild	Asymptomatic or mild symptoms; clinical or diagnostic observations only; intervention not indicated
Grade 2	Moderate	Local or noninvasive intervention indicated; limiting age-appropriate instrumental ADL*
Grade 3	Severe	Severe or medically significant but not immediately life-threatening; hospitalization or prolongation of hospitalization indicated; disabling; limiting self-care ADL**
Grade 4	Life-threatening	Urgent intervention indicated
Grade 5	Death	Death related AE

* Activities of Daily Living (ADL) Instrumental ADL refer to opening preparing meals, shopping for groceries or clothes, using the telephone, managing money, etc.

** Self-care ADL refer to bathing, dressing and undressing, feeding self, using the toilet, taking medications, and not bedridden.

7.3. Investigator Requirements and Instructions for Reporting Adverse Events and Serious Adverse Events to Gilead

Requirements for Collection Prior to Study Drug Initiation:

After informed consent, but prior to initiation of study medication, the following types of events should be reported on the case report form (CRF/eCRF): all SAEs and adverse events related to protocol-mandated procedures.

Adverse Events

Following initiation of study medication, collect all AEs, regardless of cause or relationship, until 30-days after last administration of study IMP must be reported to the CRF/eCRF database as instructed.

All AEs should be followed up until resolution or until the adverse event is stable, if possible. Gilead Sciences may request that certain AEs be followed beyond the protocol defined follow up period.

Serious Adverse Events

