7. SAFETY ANALYSES

The safety analyses will be performed for the placebo-controlled treatment period up to Week 24, and for the entire study duration. Analyses for these periods will be presented by the treatment groups specified in Section 3.

For the analyses of adverse events (AEs) that include data after Week 24 the exposure-adjusted analyses will be presented.

For the AEs, laboratory results and concomitant medication data, the collection/start date will be used to determine which reporting period the record belongs to. For other parameters collected on CRFs, the nominal visits will be used.

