7.1.5. Treatment-Emergent Adverse Events

7.1.5.1. Definition of Treatment-Emergent Adverse Events

Treatment-emergent adverse events (TEAEs) of the entire study duration are defined as 1 or both of the following:

- Any AEs with an onset date on or after any study drug start date and no later than 30 days after permanent discontinuation of any study drug
- Any AEs leading to premature discontinuation of study drug.

TEAEs up to Week 24 are defined as 1 or both of the following:

- Any AEs with an onset date on or after Day 1 and no later than the day before the Week 24 treatment start date.
- For subjects who discontinued treatment prior to Week 24 visit, any AEs with an onset date no later than 30 days after permanent discontinuation of study drug

TEAEs of active treatment are defined similarly as the definition of the entire study duration, except that active study drug instead of any study drug will be used:

- Any AEs with an onset date on or after the first dose of active study drug and no later than 30 days after permanent discontinuation of active study drug.

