7.1.6. Summaries of Adverse Events and Deaths

TEAEs will be summarized based on the Safety Analysis Set.

The tables will be presented by treatment period: placebo-controlled period (up to Week 24) and active treatment period. The overall summary of TEAEs will also be provided for the entire study duration.

The number and percentage of subjects who experienced at least 1 TEAE will be provided and summarized by SOC, HLT, PT, and treatment group. For other AEs described below, summaries will be provided by SOC, PT, and treatment group:

- All TEAEs
- TEAEs of Grade 3 or higher (by maximum severity)
- All TE treatment-related AEs
- TE treatment-related AEs of Grade 3 or higher (by maximum severity)
- All TE SAEs
- All TE treatment-related SAEs
- All TEAEs leading to premature discontinuation of study drug
- All TEAEs leading to premature discontinuation of study
- All TEAEs leading to death (i.e. outcome of death)

A brief, high-level summary of AEs described above will be provided by treatment group and by the number and percentage of subjects who experienced the above AEs. All deaths observed in the study will also be included in this summary.

Multiple events will be counted only once per subject in each summary. Adverse events will be summarized and listed first in alphabetic order of SOC and HLT within each SOC (if applicable), and then by PT in descending order of total frequency within each SOC. For summaries by severity grade, the most severe grade will be used for those AEs that occurred more than once in an individual subject during the study.

In addition to the above summary tables, all TEAEs and TE treatment-related AEs will be summarized by PT only, in descending order of total frequency.

The data listings will be provided for the following:

- All AEs, indicating whether the event is treatment emergent

- All AEs of Grade 3 or higher
- SAEs
- Deaths
- AEs leading to premature discontinuation of study drug
- AEs leading to premature discontinuation of study

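### If a site keeps one record per episode, an AE that starts on placebo and turns severe or serious after the Week 24 switch is tabulated under Placebo and missed by the active-treatment tables

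*SAP*

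**What the plan says.** - **Assignment to period.** SAP 7 states that for AEs "the collection/start date will be used to determine which reporting period the record belongs to".
- **Up to Week 24.** SAP 7.1.5.1 counts "Any AEs with an onset date on or after Day 1 and no later than the day before the Week 24 treatment start date", with a further criterion for subjects who stopped treatment before that visit.
- **Active treatment.** The lead-in in SAP 7.1.5.1 reads "TEAEs of active treatment are defined similarly as the definition of the entire study duration, except that active study drug instead of any study drug" is to be used. One bullet follows: "Any AEs with an onset date on or after the first dose of active study drug", with a window that closes 30 days after active dosing stops for good. The entire-study definition that the lead-in points to has a second criterion, "Any AEs leading to premature discontinuation of study drug", which is not printed again here.
- **Grade.** Protocol 7.2.2: "For each episode, the highest grade attained should be reported". For recurring AEs, SAP 7.1.6 says that "the most severe grade will be used for those AEs that occurred more than once in an individual subject during the study". The reference is to the study, not the period.
- **Tables.** SAP 7.1.6 plans AE tables for the placebo-controlled and active treatment periods. For the entire study it adds an overall TEAE summary. It also plans listings of all AEs, Grade 3 or higher AEs, SAEs, and AEs that ended study drug.
- **Laboratory data.** SAP 7.2 and 7.2.2.1 reset the baseline at the first active dose for subjects who began on placebo.

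**The concern.** Every placebo subject who continues changes treatment at Week 24, so an episode can straddle the switch. Onset decides where the episode is counted, while its recorded severity may have been reached later, on a different drug. The rules for onset and for grade then describe different exposures.

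The by-period tables of Grade 3 or higher AEs, SAEs and discontinuations are where a reader judges each drug, and safety and tolerability is a secondary objective. In those tables, a severe or serious state reached on filgotinib, lanraplenib or tirabrutinib would be shown as a placebo event. The SAP handles the same situation differently for laboratory abnormalities, where worsening on active drug is caught. That suggests the AE rule was not thought through for the switch.

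**Working it through.** The documents give no figure on this point, so there is nothing to reproduce. The check is a trace through the rules, followed by the size per affected subject.

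**Rule trace.** Take an AE that starts on placebo before Week 24 at Grade 1, is still ongoing at the switch, and stays on one record.

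| After the switch it... | Placebo-controlled table | Active-treatment table | Entire-study overall summary and listings |
|---|---|---|---|
| reaches Grade 3 | Placebo, Grade 3 | absent | present |
| becomes serious | Placebo, SAE | absent | present |
| ends active drug | Placebo, discontinuation AE | absent by the bullet, present by the lead-in | present |

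Column two follows because onset lies in the Week 24 window and the record carries its highest grade and final outcome. No text limits grade, seriousness or action taken to the period. Column three follows because onset precedes the first active dose and neither the lead-in nor the bullet has a worsening criterion. Column four follows because onset is after the start of study drug.

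**The discontinuation row.** Read with the entire-study definition, the lead-in carries the discontinuation criterion over, with active drug substituted. Read alone, the bullet omits it. Two programmers could build different tables from the same section. Protocol 8.6.2 has both criteria, and SAP 7.7 declares no departure from the protocol's safety analyses.

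**Size per affected subject.** Inputs: 35 per arm (Protocol 3.2) and 1:1:1 re-randomization of placebo (Protocol 3.1). Assumption: no dropout.

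- Placebo subjects moving to each drug: 35/3 = 11.7
- Subjects per drug with active exposure: 35 + 11.7 = 46.7, of whom 11.7/46.7 = 25% came from placebo
- Placebo column: 1/35 = 2.9 points too high
- Pooled active-drug column: 1/46.7 = 2.1 points too low
- A switch group shown alone: 1/11.7 = 8.6 points too low

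For a range of one to three affected subjects, all on one drug (an assumption, since the documents give no rates):

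| Affected subjects | Placebo column | Pooled active-drug column |
|---|---|---|
| 1 | +2.9 | -2.1 |
| 2 | +5.7 | -4.3 |
| 3 | +8.6 | -6.4 |

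**Effect on the difference.** The Week 24 onset rule and the highest-grade rule apply to all four arms. Let a and p be the numbers of subjects in one active arm and in placebo whose pre-Week-24 AE becomes severe only after Week 24. The active-minus-placebo difference moves by (a - p)/35. It is zero when a = p, and the documents give neither number.

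**The case against.** Five points can be made on the other side.

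1. *The lead-in governs.* A reader might infer from the single bullet that AEs ending active treatment are excluded. The documents do not settle that, because the lead-in says only the drug changes. This stands: the discontinuation part is a contradiction to reconcile, not an established exclusion.
2. *Nothing is lost from the report.* This also stands. The event remains in the entire-study overall summary, for which SAP 3.2 defines the placebo-to-drug columns, and in the listings. It is missing only from the active-treatment tables. SAP 3.2 sets no separate grouping for that period, so the 8.6-point figure applies only if a switch group is shown alone there.
3. *All arms absorb late worsening.* A reader might infer that the rule systematically flatters the active drugs by inflating placebo. That would require assuming no late worsening in subjects on active drug from Day 1, and nothing in the documents supports it. What remains specific to placebo is that the treatment is wrong. In the original active arms late worsening falls in the wrong period but under the right drug.
4. *Sites may open a new record at worsening.* Protocol 7.1.1 counts preexisting events that worsen as AEs, and recording details are left to the eCRF completion guidelines, which are not among the documents. The finding is therefore conditional. Neither document requires a new record for an on-study episode that worsens after the switch.
5. *The Week 24 report is largely spared.* Worsening after the data snapshot cannot enter it. Only placebo subjects enrolled early enough to have active-drug follow-up by then can contribute. The full effect falls in the final analysis.

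**Conclusion.** The concern holds in a limited form. Under the written rules, and if one record is kept per episode, an AE that begins on placebo and becomes Grade 3 or higher or serious on active drug is attributed to placebo at its post-switch severity and does not reach the active-treatment tables. For AEs that end active drug, SAP 7.1.5.1 gives two answers.

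With 35 per arm and no dropout, each misattributed subject is visible in rare-event rows at the sizes shown above. How many there would be cannot be derived from the documents, nor can the direction or size of any net change in active-minus-placebo differences. This is a correction to make before the final tables are programmed. It is not evidence that the safety comparison is biased in a known direction.

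**What to change.** 1. **SAP 7.1.5.1, active treatment.** Make the bullet agree with its lead-in by restating the discontinuation criterion for active drug. Add AEs with earlier onset that worsen in grade or become serious once active dosing has begun.
2. **Placebo-controlled tables, all four arms.** Do not count an AE as ending treatment when its drug-stop date is on or after the Week 24 treatment start. Use the grade and seriousness reached before that date where they are recorded.
3. **eCRF completion guideline.** Have any AE that worsens after the Week 24 first dose entered as a new record, for every subject. Applying it to all arms keeps the blind.

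These changes affect tabulation and recording only, not clinical management. The discontinuation parts need only the recorded AE action and the dosing dates, and the Week 24 start date is already on the CRF. The cost is SAP wording, a programming rule and one line in the guideline. An AE may appear in both period tables, which a footnote can explain. Because only the highest grade per episode is required, records already entered may need queries for the date of worsening, and some pre-switch grades may not be recoverable.

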7.1.5.2. Incomplete Dates

If the onset date of the AE is incomplete and the AE stop date is not prior to the first dosing date of study drug, then the month and year (or year alone if month is not recorded) of onset determine whether an AE is treatment emergent. The event is considered treatment emergent if both of the following 2 criteria are met:

- The AE onset is the same as or after the month and year (or year) of the first dosing date of study drug, and
- The AE onset date is the same as or before the month and year (or year) of the date corresponding to 30 days after the date of the last dose of study drug

An AE with completely missing onset and stop dates, or with the onset date missing and a stop date later than the first dosing date of study drug, will be considered to be treatment emergent. In addition, an AE with the onset date missing and incomplete stop date with the same or later month and year (or year alone if month is not recorded) as the first dosing date of study drug will be considered treatment emergent.

7.1.6. Summaries of Adverse Events and Deaths

TEAEs will be summarized based on the Safety Analysis Set.

The tables will be presented by treatment period: placebo-controlled period (up to Week 24) and active treatment period. The overall summary of TEAEs will also be provided for the entire study duration.

The number and percentage of subjects who experienced at least 1 TEAE will be provided and summarized by SOC, HLT, PT, and treatment group. For other AEs described below, summaries will be provided by SOC, PT, and treatment group:

- All TEAEs
- TEAEs of Grade 3 or higher (by maximum severity)
- All TE treatment-related AEs
- TE treatment-related AEs of Grade 3 or higher (by maximum severity)
- All TE SAEs
- All TE treatment-related SAEs
- All TEAEs leading to premature discontinuation of study drug
- All TEAEs leading to premature discontinuation of study
- All TEAEs leading to death (i.e. outcome of death)

A brief, high-level summary of AEs described above will be provided by treatment group and by the number and percentage of subjects who experienced the above AEs. All deaths observed in the study will also be included in this summary.

Multiple events will be counted only once per subject in each summary. Adverse events will be summarized and listed first in alphabetic order of SOC and HLT within each SOC (if applicable), and then by PT in descending order of total frequency within each SOC. For summaries by severity grade, the most severe grade will be used for those AEs that occurred more than once in an individual subject during the study.

In addition to the above summary tables, all TEAEs and TE treatment-related AEs will be summarized by PT only, in descending order of total frequency.

The data listings will be provided for the following:

- All AEs, indicating whether the event is treatment emergent

- All AEs of Grade 3 or higher
- SAEs
- Deaths
- AEs leading to premature discontinuation of study drug
- AEs leading to premature discontinuation of study

7.1.7. Adverse Events of Special Interest

Adverse events of interest will be identified by the use of either SMQs or MSTs. However, should additional cases not detected by the predefined search term listings be identified during the clinical review process, these cases will also be reported by respective category.

Adverse events of interest include:

- All infections (defined as all PTs within the Infections and Infestations SOC)
 - Infections of interest as defined below
 - Herpes zoster
 - Active tuberculosis
 - Opportunistic infections
 - Hepatitis B (HBV) or C (HCV) infections
- Serious infections (defined as all PTs within the Infections and Infestations SOC that are SAEs)
- Venous thrombotic events
- Malignancies
- Gastrointestinal (GI) perforations
- Liver transaminase elevation
- Bleeding or Haemorrhage (SMQ)
- Renal toxicity (MST)
- Cytopenia
 - HLT Anaemia deficiencies

- HLT Anaemias haemolytic immune
- HLT Anaemias haemolytic mechanical factor
- HLT Anaemias haemolytic NEC (not elsewhere classified)
- HLT Anaemias NEC
- HLT Leukopenias NEC
- HLT Marrow depression and hypoplastic anaemias
- HLT Neutropenias
- HLT Thrombocytopenias
- but excluding PTs in:
 - HLT Anaemias congenital (excluding haemoglobinopathies)
 - HLT Anaemias due to chronic disorders
 - HLT Anaemias haemolytic immune newborn
- Serious potential major adverse cardiovascular events (MACE) including the following:
 - Cardiovascular events
 - Myocardial infarction
 - Hospitalization for unstable angina
 - Transient ischemic attack
 - Stroke
 - Hospitalization for cardiac failure
 - Percutaneous coronary intervention
- Noninfectious Diarrhoea (SMQ)

Potential serious MACE events will not be adjudicated.

The number and percentage of patients with aforementioned events of special interest will be provided by the PT term for each category of AE of special interests.

A by-subject listing for all patients having AE of special interests at any time will be provided for each AE of special interests.

7.2. Laboratory Evaluations

Laboratory data collected during the study will be analyzed and summarized using both quantitative and qualitative methods. Summaries of laboratory data will be provided for the Safety Analysis Set and will include data collected up to the last dose of study drug plus 30 days for subjects who have permanently discontinued study drug, or all available data at the time of the database snapshot for subjects who were ongoing at the time of an interim analysis. The analysis will be based on values reported in conventional units. When values are below the LOQ, they will be listed as such, and the closest imputed value will be used for the purpose of calculating summary statistics as specified in Section 3.7. Hemolyzed test results will not be included in the analysis, but they will be listed in by-subject laboratory listings.

A baseline laboratory value for the placebo-controlled and entire study period will be defined as the last nonmissing measurement obtained on or prior to the date/time of first dose of any study drug. For the active treatment period, the baseline for the subjects originally randomized to placebo will be the latest measurement before or on the day when the first dose of active study treatment is administered.

A by-subject listing for laboratory test results will be provided by subject ID number and visit in chronological order for hematology, serum chemistry, and urinalysis separately. Values falling outside of the relevant reference range and/or having a severity grade of 1 or higher on the CTCAE severity grade will be flagged in the data listings, as appropriate.

No formal statistical testing is planned.

7.2.1. Summaries of Numeric Laboratory Results

Descriptive statistics will be provided by treatment group for each laboratory test specified in the study protocol as follows:

- Baseline values
- Values at each postbaseline visit
- Change and percentage change from baseline at each postbaseline visit.

Descriptive statistics will be provided by treatment group for the following laboratory tests:

- Hematology
 - Hematocrit
 - Hemoglobin
 - Platelet count
 - Red blood cell count

- White blood cell (WBC) count
- Mean corpuscular volume
- Lymphocytes
- Monocytes
- Neutrophils
- Eosinophils
- Basophils
- Chemistry
 - Alanine aminotransferase (ALT)
 - Aspartate aminotransferase (AST)
 - Alkaline phosphatase (ALP)
 - Total bilirubin
 - Serum creatinine
 - Creatinine clearance by Cockcroft-Gault formula
 - Creatinine phosphokinase (CPK)
 - Glucose
 - Triglycerides
 - Total cholesterol
 - High Density Lipoprotein (HDL)
 - LDL (Low Density Lipoprotein)
 - LDL/HDL ratio

Change from baseline to a postbaseline visit will be defined as the visit value minus the baseline value. The mean, median, Q1, Q3, minimum, and maximum values will be displayed to the reported number of digits; SD values will be displayed to the reported number of digits plus 1.

Median (Q1, Q3) of the observed values for the laboratory tests specified above will be plotted using a line plot by treatment group and visit.

In the case of multiple values within the visit, data will be selected for analysis as described in Section 3.8.3

